5.1 Eligibility

5.1.1 Inclusion criteria

- Patients with metastatic colorectal cancer who have progressed on, or are ineligible for standard therapy such as fluoropyrimidines, oxaliplatin, irinotecan, endothelial growth factor (VEGF) inhibitors such as bevacizumab, and anti-EGFR antibodies where appropriate, but are suitable candidates for regorafenib treatment.
- Patients with radiographically measurable biopsy-accessible disease.
- Patients who have an Eastern Cooperative Oncology Group (ECOG) performance score of 0 or 1.
- Age \geq 18 years.
- Life expectancy of at least 12 weeks (3 months).
- Subjects must be able to understand and be willing to sign the written informed consent form. Ideally, a signed informed consent form will be appropriately obtained prior to the conduct of any trial-specific procedure. However, if patients have had standard of care assessments performed within the screening period, but before the consent was signed, these will be admissible.
- Adequate bone marrow, liver and renal function as assessed by the following laboratory requirements:
 - Total bilirubin \leq 1.5 x the upper limits of normal (ULN)
 - Alanine aminotransferase (ALT) and aspartate amino-transferase (AST) \leq 2.5 x ULN (\leq 5 x ULN for subjects with liver involvement of their cancer)
 - Alkaline phosphatase limit \leq 2.5 x ULN (\leq 5 x ULN for subjects with liver involvement of their cancer)
 - Serum creatinine \leq 1.5 x the ULN
 - For subjects with liver metastases, AST and ALT \leq 5 X the upper normal limit of institution's normal range, and Non-fasting bilirubin 1.5 - 3.0 X the upper normal limit of institution's normal range are acceptable
 - As patients will undergo tissue biopsy, their international normalized ratio (INR)/ Partial thromboplastin time (PTT) has to be \leq 1.5 x ULN. In addition, a platelet count $>$ 100000 /mm³ and absolute neutrophil count (ANC) \geq 1500/mm³ is necessary.
-

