
3
 
Systolic BP \geq 160 mmHg or diastolic BP \geq 100 mmHg OR More than one drug or more intensive therapy than previously used indicated
	
Treat with the aim to achieve diastolic BP \leq 90 mm Hg: Start anti-hypertensive medication
 
AND/OR Increase current anti-hypertensive medication
 
AND/OR Add additional anti-hypertensive medications.
	
 • Hold regorafenib until diastolic BP \leq 90 mm Hg, and if symptomatic, until symptoms resolve.^a • When regorafenib is restarted, continue at the same dose level. • If BP is not controlled with the addition of new or more intensive therapy, reduce by 1 dose level.^b • If Grade 3 hypertension recurs despite dose reduction and antihypertensive therapy, reduce another dose level.^c

4
 
Life-threatening consequences (e.g., malignant hypertension, transient or permanent neurologic deficit, hypertensive crisis)
	
Per institutional guidelines
	
Discontinue therapy

a. Patients requiring a delay of >4 weeks should go off protocol therapy
 
b. If BP remains controlled for at least one cycle, dose re-escalation permitted per investigator's discretion.
 
c. Patients requiring >2 dose reductions should go off protocol therapy.
		

Table 6-4: Management of Treatment-Emergent Hypertension

Liver Function Abnormalities

For patients with observed worsening of serum liver tests considered related to regorafenib (i.e. where no alternative cause is evident, such as post-hepatic cholestasis or disease progression), the dose modification and monitoring advice in Table 6-5 should be followed.

Regorafenib is a UGT1A1 inhibitor. Mild, indirect (unconjugated) hyperbilirubinemia may occur in patients with Gilbert’s syndrome.

Table 6.5: Recommended measures and dose modifications in case of drug-related liver function test abnormalities

Observed elevations of ALT and/or AST	Occurrence	Recommended measures and dose modification
≤ 5 times upper limit of normal (ULN) (maximum Grade 2)	Any occurrence	Continue Regorafenib treatment. Monitor liver function weekly until transaminases return to < 3 times ULN (Grade 1) or baseline.

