>5 times ULN to ≤ 20 times ULN (Grade 3)	1 st occurrence	Interrupt Regorafenib treatment. Monitor transaminases weekly until return to < 3 times ULN or baseline. Restart: If the potential benefit outweighs the risk of hepatotoxicity, re-initiate Regorafenib treatment, reduce dose by 40 mg (one tablet), and monitor liver function weekly for at least 4 weeks.
	Re-occurrence	Discontinue treatment with Regorafenib permanently.
>20 times ULN (Grade 4)	Any occurrence	Discontinue treatment with Regorafenib permanently.
>3 times ULN (Grade 2 or higher) with concurrent bilirubin >2 times ULN	Any occurrence	Discontinue treatment with Regorafenib permanently. Monitor liver function weekly until resolution or return to baseline. Exceptions: patients with Gilbert’s syndrome who develop elevated transaminases should be managed as per the above outlined recommendations for the respective observed elevation of ALT and/or AST.

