8.4 Safety

All subjects who receive at least one dose of study treatment will be valid for the safety analysis.

All observations pertinent to the safety of the study treatment will be recorded and included in the final report.

Safety variables include the following: AEs, laboratory changes (complete blood counts, electrolytes, chemistry, and coagulation), changes in vital signs (blood pressure, heart rate, respiratory rate, and temperature) and ECG and, in some instances, changes in chest x-ray images, as produced at the investigator's discretion (e.g., for evaluation for pneumonia).

All AEs whether considered drug-related or not, will be reported in with a diagnosis, start/stop dates, action taken, whether treatment was discontinued, any corrective measures taken, outcome, and other possible causes. For all events, the relationship to treatment and the intensity of the event will be determined by the investigator.

This trial will use the NCI-CTCAE v4.0 criteria for assessment of toxicity and SAE reporting with regard to toxicity grade.

8.4.1 Data safety Monitoring Plan:

The Georgetown Lombardi Comprehensive Cancer Center will be responsible for the data and safety monitoring of this multi-site trial. As this study is an investigator initiated exploratory study utilizing an FDA approved drug it is considered a moderate risk study which requires real-time monitoring by the PI and study team and semi-annual reviews by the LCCC Data and Safety Monitoring Committee (DSMC).

The Principal Investigator and the Co-Investigators will review the data including safety monitoring at their weekly institution based disease group meetings and on monthly teleconferences.

All Severe Adverse Events (SAEs) are required to be reported to the IRB. Based on SAEs, the IRB retains the authority to suspend further accrual pending more detailed reporting and/or modifications to further reduce risk and maximize the safety of participating patients.

Progress on the trial and the toxicities experienced will be reviewed by the LCCC Data and Safety Monitoring Committee every 6 months from the time the first patient is enrolled on the study. Results of the DSMC meetings will be forwarded to the IRB with recommendations regarding need for study closure.

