Safety analyses will be performed in all treated subjects. Descriptive statistics of safety will be presented using National Cancer Institute (NCI) Common Terminology Criteria for Adverse Events (CTCAE) version 4.0. All on-study AEs, treatment-related AEs, SAEs, and treatment-related SAEs will be tabulated using worst grade per NCI CTCAE v 4.0 criteria by system organ class and preferred term. On-study lab parameters including hematology, chemistry, liver function, and renal function will be summarized using worst grade NCI CTCAE v 4.0 criteria. For continuous safety variables, mean, standard deviation, and 95% confidence interval will be calculated at baseline and each visit.

Descriptive statistics (N, percentage for categorical variables and N, mean, std, median, min, max for continuous variables) will be used to summarize the activation status of phosphoproteins, presence and level of mutated DNA in serum at baseline, 4 and 8 weeks of study treatment. Repeated measures models may be used to explore the relationship between the level of mutated DNA in serum with clinical response.

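### Worst on-study laboratory grade is tabulated without entry grade, so Grade 1-2 and any-grade ALT/AST counts mix unchanged entry abnormality with new abnormality

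*Combined protocol and SAP*

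**What the plan says.** Section 8.4 lists, among the safety variables, "laboratory changes (complete blood counts, electrolytes, chemistry, and coagulation"). For graded laboratory values, section 9.3.2 plans this: "On-study lab parameters including hematology, chemistry, liver function, and renal function will be summarized using worst grade NCI CTCAE v 4.0 criteria". It also plans a group summary: "For continuous safety variables, mean, standard deviation, and 95% confidence interval will be calculated at baseline and each visit". I find no cross-tabulation against entry grade and no rule for counting a grade as new or worsened.

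Section 5.1.1 allows raised liver tests at entry. The ALT/AST limit is 2.5 x ULN, relaxed to "5 x ULN for subjects with liver involvement of their cancer". Alkaline phosphatase has the same two limits. Total bilirubin is limited to 1.5 x ULN, but for patients with liver metastases "Non-fasting bilirubin 1.5 - 3.0 X the upper normal limit of institution's normal range are acceptable".

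Table 6.5 in section 6.2.1 gives the ALT/AST grade boundaries. Values up to "5 times upper limit of normal (ULN) (maximum Grade 2") form its lowest row, and Grade 3 runs from above 5 to "20 times ULN (Grade 3"). The boundary between Grades 1 and 2 is in the monitoring instruction: "Monitor liver function weekly until transaminases return to < 3 times ULN (Grade 1) or baseline".

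**The concern.** A worst-grade count is not a change. It would come close to one if everyone entered at Grade 0, but this protocol deliberately admits patients with raised transaminases, and its separate limits for liver involvement show that such patients are expected. The trial is uncontrolled, so no comparator arm shows how much low-grade abnormality the disease alone produces. The natural reference is each patient's own entry grade. Table 6.5 already uses it for dosing, since recovery there may mean return to baseline. The laboratory table does not.

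What is at stake is one descriptive display. A reader who takes its Grade 1-2 or any-grade ALT/AST rows as liver effects of treatment could attribute to regorafenib abnormalities that were present before the first dose.

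**Working it through.** The documents give no laboratory grade counts, so there is no figure of the plan's to reproduce. The check compares the entry limits with the grade limits and then gives a sense of scale.

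**1. Entry limits against grade limits (ALT/AST)**

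| Value | Source | Grade by Table 6.5 |
|---|---|---|
| up to 2.5 x ULN | entry limit, 5.1.1 | at most 1 (below 3 x ULN) |
| up to 5 x ULN | entry limit with liver involvement, 5.1.1 | at most 2 |
| above 5 to 20 x ULN | not permitted at entry | 3 |
| above 20 x ULN | not permitted at entry | 4 |

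Permitted entry values can be Grade 1 or 2 but never Grade 3 or 4. Every Grade 3/4 ALT/AST value in an eligible patient is therefore a worsening, although the worst-grade table does not show by how much.

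**2. Scale for Grade 2**

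N = 40 is from section 9.4. The number entering with raised values is not given. I assume k = 4, 8 or 12 patients at 4 x ULN (Grade 2) and the other 40 - k at 1 x ULN.

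- *Nobody changes.* The table shows k/40 at Grade 2: 4 (10%), 8 (20%) or 12 (30%). Patients who worsened: 0/40.
- *Eight normal patients each rise once to 4 x ULN*, two at each of C1D14, C2D1, C2D14 and C3D1. The table shows k + 8 = 12, 16 or 20 at Grade 2. Patients who worsened: 8/40 in every case.

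**3. Whether the visit means recover the eight**

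Baseline mean = [4k + (40 - k)]/40.

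- k = 4: 52/40 = 1.30 (SD 0.91)
- k = 8: 64/40 = 1.60 (SD 1.22, t-based 95% CI 1.21 to 1.99)
- k = 12: 76/40 = 1.90 (SD 1.39)

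Two more patients at 4 x ULN move a visit mean by 2 x 3/40 = 0.15, to 1.45, 1.75 or 2.05. For k = 8 the new interval is 1.33 to 2.17 (SD 1.32), which overlaps the baseline interval heavily. Nothing in these means says that eight separate patients worsened.

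**4. Scale for the any-grade row, under different assumptions**

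Let q be the share entering at Grade 1-2, p the probability of a new or worse grade, and s the probability that an unchanged entry abnormality is seen again on study. Then:

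- new or worsened = Np
- tabulated any grade = Np + Nq(1 - p)s
- unchanged entry abnormality in the row = Nq(1 - p)s

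With N = 40 and s = 1:

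| p | q | New or worsened | Tabulated | Unchanged share |
|---|---|---|---|---|
| 20% | 10% | 8 | 11.2 | 29% |
| 20% | 30% | 8 | 17.6 | 55% |
| 20% | 60% | 8 | 27.2 | 71% |
| 40% | 10% | 16 | 18.4 | 13% |
| 40% | 30% | 16 | 23.2 | 31% |
| 40% | 60% | 16 | 30.4 | 47% |

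If s = 0.8, the unchanged share falls to 24%, 49% and 66% (p = 20%) or 11%, 26% and 42% (p = 40%). Across all these settings, the unchanged entry abnormalities counted run from 40 x 0.1 x 0.6 x 0.8 = 1.9 to 40 x 0.6 x 0.8 x 1 = 19.2 patients.

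**The case against.** The strongest reply is that nothing in 9.3.2 is false. The section never calls the worst-grade table treatment-emergent, and the reference to laboratory changes in 8.4 can be served by other outputs. Section 8.4.3 counts abnormal laboratory findings as adverse events and limits events to conditions that began or deteriorated after consent. Section 7.2.1.5 sends clinically significant out-of-range values to the adverse event record, and 9.3.2 tabulates those events by worst grade. On this view a per-patient count of worsening exists already, and a shift table is a matter of taste.

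Much of this stands, and it is why the stakes are low. It does not cover the grades in question. The route through 7.2.1.5 needs an investigator's judgement of clinical significance. It also needs criteria said to be in section 9.4, which is the sample size section. A low-grade rise not judged clinically significant need not appear in the adverse event tables.

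The second reply is that the example of visit means depends on its pattern. If all eight rises coincided or persisted, the mean would move 8 x 3/40 = 0.60 x ULN, from 1.60 to 2.20. It also keeps all 40 patients to C3D1, although section 1.2.2 quotes a median progression-free survival of 1.9 months on regorafenib. Both remarks are fair. Even so, a mean that moves by 0.60 does not count the patients who worsened or show their entry grade.

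Third, the prevalences are invented. They are assumptions, shown as ranges. The overlap between entry limits and Grades 1-2 does not depend on them; only its size does.

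**Conclusion.** The concern holds and is minor. Followed as written, 9.3.2 puts unchanged and new ALT/AST abnormality in the same Grade 1-2 cells, so those cells and the any-grade row cannot be read as on-treatment change. This follows from the protocol's own limits and needs no outside source.

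How many patients are affected cannot be taken from the documents, because the distribution of entry grades is not given. Under the assumed ranges it is anywhere from about 2 to about 19 of 40 in the any-grade row.

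The conclusion is limited to low-grade ALT/AST in one descriptive table. Grade 3/4 ALT/AST counts are not mixed in eligible patients. The Grade 3/4 adverse event endpoint is largely protected by the definition in 8.4.3. No test, sample size or dose decision rests on this table. For alkaline phosphatase and bilirubin the documents permit raised entry values but give no grade cut-offs, so no mixing is claimed in figures for them.

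**What to change.** In section 9.3.2, keep the worst-grade and continuous summaries and add a shift table for ALT, AST, alkaline phosphatase and bilirubin: baseline CTCAE grade by worst on-treatment grade. Take baseline as the last pre-dose value, which is the rule section 7.1 already sets. Report the number of patients who worsen by at least one grade, and show Grade 3 or worse separately. Alkaline phosphatase and bilirubin belong in the table because section 5.1.1 allows entry values up to 5 x and 3 x ULN respectively in patients with liver disease.

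The cost is one sentence in 9.3.2 and one extra descriptive table. Chemistry at screening, C1D1 and later visits is already collected under section 7.2.1.5, so no new sample, visit or data field is needed.

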1.2.2 Clinical experience

Two phase III global randomized studies have evaluated the efficacy of regorafenib. The CORRECT (Patients with metastatic colorectal cancer treated with regorafenib or placebo after failure of standard therapy) trial is an international, multicenter, randomized, double-blind, placebo-controlled study that enrolled 760 patients with mCRC whose disease has progressed after approved standard therapies. Metastatic colorectal cancer patients were randomized to regorafenib plus best supportive care (BSC) or placebo plus BSC. Treatment cycles consisted of 160 mg of regorafenib (or matching placebo) once daily for three weeks on / one week off plus BSC. The primary endpoint of this trial was overall survival. Secondary endpoints included progression-free

survival, objective tumor response rate and disease control rate. The safety and tolerability of the two treatment groups were also compared.

At a preplanned second interim analysis, there was a statistically significant survival benefit for regorafenib. The estimated hazard ratio for overall survival was 0.773 (95% confidence interval [CI], 0.635 to 0.941; 1-sided $p = .0051$). Patients treated with regorafenib had a median overall survival of 6.4 months, compared with 5.0 months for placebo — a 29% increase in survival. In addition to improved overall survival, progression-free survival was superior; median progression-free survival was 1.9 months (95% CI, 1.88 to 2.17) for regorafenib and 1.7 months (95% CI, 1.68 to 1.74) for placebo. The estimated hazard ratio for progression-free survival was 0.493 (95% CI, 0.418 to 0.581; 1-sided $p < .000001$). There was a substantial difference in disease control rate in the regorafenib and placebo groups (44% vs. 15%; $p < .000001$). Regorafenib demonstrated comparable efficacy benefits across patient subgroups analyzed including age, number of metastases, number of lines of prior therapy, and *kras* status.

The most frequent grade 3+ adverse events in the regorafenib group were hand–foot skin reaction (17%), fatigue (15%), diarrhea (8%), hyperbilirubinemia (8%), and hypertension (7%). The efficacy and safety from the CORRECT study supported FDA approval in September 2012.

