- Keratolytic creams (e.g. urea-based creams, salicylic acid 6%) may be used sparingly and only to affected (hyperkeratotic) areas.
- Alpha hydroxyl acids (AHA) based creams may be applied liberally 2 times a day. Approximately 5% to 8% provides gentle chemical exfoliation.
- Topical analgesics (e.g. lidocaine 2%) are to be considered for pain control.
- Topical corticosteroids like clobetasol 0.05% should be considered for subjects with Grade 2 or 3 HFSR. Avoid systemic steroids.

Tender areas should be protected as follows:

- Use socks/gloves to cover moisturizing creams
- Wear well-padded footwear
- Use insole cushions or inserts (e.g. silicon, gel)
- Foot soaks with tepid water and Epsom salts

Hypertension

Hypertension is a known AE associated with regorafenib treatment. Subject will have their blood pressure measured at least weekly at the study site during the first 6 weeks of treatment. If additional blood pressure measurements are done outside the study site, and the blood pressure is > 140 mm Hg systolic or > 90 mm Hg diastolic (NCI CTCAE v4.0), then the subject must contact study personnel. The management of hypertension, including the choice of antihypertensive medication, will be performed according to local standards and to the usual practice of the investigator. Every effort should be made to control blood pressure by medical means other than study drug dose modification. If necessary, Table 6-4 outlines suggested dose reductions.

Grade (CTCAE v4.0)	Antihypertensive Therapy	Regorafenib Dosing

1
 
Prehypertension (systolic BP 120 - 139 mmHg or diastolic BP 80 - 89 mmHg)
	
None
	
 • Continue regorafenib • Consider increasing blood pressure (BP) monitoring

2
 
Systolic BP 140 - 159 mmHg or diastolic BP 90 - 99 mmHg, OR Symptomatic increase by > 20 mmHg (diastolic) if previously within normal limits
	
 • Treat with the aim to achieve diastolic BP \leq 90 mm Hg: • If BP previously within normal limits, start anti-hypertensive monotherapy • If patient already on anti-hypertensive medication, titrate up the dose. 	
 • Continue regorafenib • If symptomatic, hold regorafenib until symptoms resolve AND diastolic BP \leq 90 mm Hg^a. When regorafenib is restarted, continue at the same dose level.

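### Section 8.4 names changes in vital signs and laboratory values as safety variables, but section 9.3.2 plans only visit-by-visit means, with no within-patient change and no count per visit (minor)

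*Combined protocol and SAP*

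**What the plan says.** Section 8.4 lists the safety variables. Besides adverse events they include "laboratory changes (complete blood counts, electrolytes, chemistry, and coagulation" and "changes in vital signs (blood pressure, heart rate, respiratory rate, and temperature) and ECG". Both are worded as changes.

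Section 9.3.2 gives the analyses. The population is clear: "Safety analyses will be performed in all treated subjects". For continuous variables the whole plan is "For continuous safety variables, mean, standard deviation, and 95% confidence interval will be calculated at baseline and each visit". That sentence has no change from baseline, no number of patients per visit and no rule for a patient with no value at a visit.

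It is not the only safety summary. For laboratory values: "On-study lab parameters including hematology, chemistry, liver function, and renal function will be summarized using worst grade NCI CTCAE v 4.0 criteria". Adverse events and serious adverse events "will be tabulated using worst grade per NCI CTCAE v 4.0 criteria by system organ class and preferred term".

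Section 7.2.1 schedules vital signs, hematology and chemistry at screening, C1D1, C1D14, C2D1, C2D14, Day 1 of each cycle from cycle 3, and the off-study visit. Section 7.2.1.6 keeps a patient on study while disease has not progressed and treatment is tolerated, with the first scheduled response evaluation at week 8.

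**The concern.** A table with a baseline mean and a mean for each visit invites the reader to subtract one from the other. The baseline mean covers everyone treated, up to 40 patients. Later means cover only those still attending, and they are selected on progression and tolerance. The difference then reflects two things: how the remaining patients changed, and how their baseline values differed from those of the patients who left.

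The planned intervals do not help. Separate 95% intervals at baseline and at a visit do not give an interval for the change, because that also needs the within-patient correlation and the number of patients with both values.

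Vital signs matter here because the protocol itself says "Hypertension is a known AE associated with regorafenib treatment". The plan already uses suitable methods elsewhere: section 9.3.1 has a paired t-test or Wilcoxon signed rank test for biomarker change over time, and section 9.3.2 lists N in its biomarker summaries. The safety sentence has neither.

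**Working it through.** **1. Is there a figure in the plan to reproduce?** No. The documents state no retention or drop-out rate for this study. The only related inputs come from the cited phase III trial in section 1.2.2: "median progression-free survival was 1.9 months (95% CI, 1.88 to 2.17) for regorafenib", and a disease control rate of 44%.

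**2. Rough retention, if PFS stood in for staying on study.** Assume exponential PFS, S(t) = 0.5^(t / median), with median = 1.9 × 30.44 = 57.8 days (8.3 weeks).

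| Time | S(t) | Of 40 |
|---|---|---|
| 4 weeks (28 days) | 0.71 | 29 |
| 8 weeks (56 days) | 0.51 | 20 |
| 12 weeks (84 days) | 0.37 | 15 |
| 16 weeks (112 days) | 0.26 | 10 |

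Across the quoted confidence interval for the median, the week-8 value is 0.51 to 0.56, or 20 to 22 of 40. The disease control rate gives 0.44 × 40 = 17.6. So roughly half being progression-free at about week 8 is consistent with the cited trial. The smooth curve overstates loss before week 8 to the extent that progression is first found on the week-8 scan; those patients are still due at C1D14, C2D1 and C2D14.

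**3. Shift in a visit mean with no change in any patient.** Let f be the share retained and r the correlation between the baseline value and the propensity to stay, under a normal model. The mean baseline value of the retained patients differs from that of all patients by

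shift (in baseline SDs) = r × φ(z) / f, with z = Φ⁻¹(1 − f).

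At f = 0.50, φ(0)/0.50 = 0.399/0.50 = 0.798. The documents give no r, so these are assumptions:

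| r | f = 0.44 | f = 0.50 | f = 0.51 |
|---|---|---|---|
| 0 | 0 | 0 | 0 |
| 0.1 | 0.09 | 0.08 | 0.08 |
| 0.3 | 0.27 | 0.24 | 0.23 |
| 0.5 | 0.45 | 0.40 | 0.39 |

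A negative r gives the same sizes with the opposite sign. The shift can therefore mask a rise, exaggerate one, or be absent.

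**4. What pairing does.** Change computed in patients with both values removes this shift exactly, because the same patients supply both means. It can also be more precise. With an assumed within-patient correlation of 0.7, 40 values at baseline, 20 at the visit and retention unrelated to the values:

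- Difference of raw means: SE = √(1/40 + 1/20 − 2 × 0.7/40) = √0.040 = 0.200 SD.
- Paired change: SE = √(2 × (1 − 0.7)/20) = √0.030 = 0.173 SD.

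**5. What the worst-grade tables already cover.** A graded laboratory rise stays in the worst-grade table after the patient leaves. A blood pressure rise reported as hypertension reaches the adverse event table. Three things are left:

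- vital-sign measurements not reported as adverse events;
- changes below a grading threshold;
- laboratory abnormalities present at entry. Section 5.1.1 admits patients with liver involvement with ALT and AST up to 5 × ULN, and Table 6.5 labels values up to 5 × ULN as at most Grade 2. Such a patient can show a worst grade of 2 with no rise at all.

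**The case against.** Several stronger readings are tempting, and the documents do not support them.

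- **A reader might infer that laboratory values are summarized only as raw means.** They are not. Section 9.3.2 also gives worst CTCAE grade, and section 7.2.1.5 has clinically significant values recorded as adverse events. A rise past the grading threshold could not vanish because patients left. Treating hypertension does not remove it either, since the grading in Table 6-4 counts the need for more intensive therapy.
- **A reader might infer that half the patients will have dropped out by week 8.** That is progression or death in a cited trial at 160 mg; this study starts at 120 mg. Progression is not the same as missing a visit, the first scheduled scan is at week 8, and leavers are due an off-study assessment. The main loss is expected at or after that scan. Earlier losses cannot be quantified from the documents.
- **A reader might put the hidden rise at several mmHg.** With an assumed SD of 15 mmHg, r = 0.3 to 0.5 gives 0.24 × 15 = 3.6 to 0.40 × 15 = 6.0 mmHg. The documents give neither the SD nor the correlation nor its sign, and at r = 0 the shift is zero.
- **A reader might expect paired change to isolate the drug's effect.** It cannot. The Synopsis describes an uncontrolled study, the paired change is still selected on who stays, and antihypertensive treatment lowers later values in either summary.

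It is also fair that section 9.3.2 never says visit means will be subtracted. The safety endpoint in section 9.2.2 is the percentage with Grade 3/4 events plus a description of the safety profile, and no test or stopping rule uses these means. All of this stands and limits the severity. It leaves untouched the mismatch between the variables defined in section 8.4 and the analysis planned in section 9.3.2.

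**Conclusion.** The point holds in limited form. Section 8.4 defines continuous safety variables as changes, and section 9.3.2 plans no analysis of change and no count per visit. At later visits, mainly after the week-8 scan, comparing the visit mean with the all-patient baseline mean mixes within-patient change with who remains.

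The shift cannot be sized from the documents. With about half retained and an assumed correlation of 0 to 0.5 in absolute value, it is 0 to about 0.4 baseline SD, in either direction. The half-retained figure is itself borrowed from PFS in the cited trial under an exponential assumption.

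Because graded toxicity is tabulated separately, this is a minor point: a cheap improvement to a descriptive secondary summary in an exploratory study.

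**What to change.** Keep the worst-grade tables. Replace the sentence on continuous safety variables in section 9.3.2 with text to this effect:

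*For each continuous safety variable, report at each visit the number of patients with a value and, in patients with both a baseline and a visit value, their number and the mean, SD and 95% confidence interval of the change from baseline. Baseline is the last value before the first dose. Also summarize each patient's maximum on-treatment change. Off-study-visit values will be shown separately or assigned to a scheduled visit by a stated rule. Results describe within-patient change in an uncontrolled study and are not estimates of drug effect.*

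The baseline definition agrees with section 7.1. The off-study rule still has to be chosen and written down.

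The cost is SAP wording and a few more descriptive tables. Blood pressure, heart rate, temperature, hematology and chemistry are already scheduled at the visits. The events table has no ECG and schedules coagulation only at screening unless specially required, so section 9.3.2 should not promise a paired change for those two without a check on what is collected. The limits remain: the paired change is still selected on who stays and is affected by antihypertensive treatment. The table should say so.
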